8 STATISTICAL CONSIDERATIONS

8.1 Sample Size Determination

- Sample size determination is not based on statistical power calculation.

1) Neoadjuvant cohort:

The SCCHN tumor types will contain 21 HPV-positive and 21 HPV-negative evaluable subjects. MCC and cervical, vaginal, or vulvar cancers tumor types will contain 21 evaluable subjects each. A sample size of 21 can detect, with more than 66% and 89% probability, a safety event that occurs at an incident rate of 5% and 10%, respectively. Assuming 10%, 15%, and 20% for pathologic complete response rate, a sample size of 21 can detect more than 89%, 97% and 99% probability, at least one pathologic complete response respectively.

2) Recurrent/metastatic monotherapy cohort:

HPV+ SCCHN, GYN, MCC and NPC tumor types in the recurrent/metastatic cohort will contain approximately 23 subjects. Table 8.1-1 shows the probabilities of observing 0, 1 or 2 responders and ≥ 3 responders assuming 5%, 20% and 30% true response rate of ORR. Table 8.1-2 shows the two-sided 95% exact CI using Clopper-Pearson methods based on observed 3, 4 and 5 responders out of 23 subjects.

EBV+ Gastric tumor type will contain approximately 12 subjects, due to the low prevalence. Table 8.1-5 shows the precision of the estimation of ORR based on the two sided 95% exact CI using Clopper-Pearson methods based on 1, 2, 3, 4 and 5 responders out of 12 subjects.

Table 8.1-1: Probability of Observing Responses Given True ORR for Sample Size of 23 Subjects

| True ORR | Probability of observing 0, 1 or 2 responses | Probability of observing ≥ 3 responses |
|----------|--|---|
| 5% | 89.5% | 10.5% |
| 20% | 13.3% | 86.7% |
| 30% | 1.6% | 98.4% |

Table 8.1-2: Two-sided 95% Exact CI Using Clopper-Pearson Method Based on Number of Observed Responses out of 23 Subjects

| The number of observed responses | 3 | 4 | 5 |
|----------------------------------|---------------|---------------|---------------|
| Observed Response Rate | 3/23 (13.0%) | 4/23 (17.4%) | 5/23 (21.7%) |
| 95% exact CI | (2.8%, 33.6%) | (5.0%, 38.8%) | (7.5%, 43.7%) |

3) Recurrent/metastatic combination cohort:

The HPV+ SCCHN, MCC, and NPC tumor types in the recurrent/metastatic cohort will each contain approximately 40 subjects that will be enrolled to the Combo A treatment arm. Patients with cervical cancer and anogenital HPV associated tumors (vulvar/vaginal/anal canal/penile) tumor types will be randomized in a 1:1 ratio to one of two dosing schema (Combo A or Combo B).

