Each dosing schema will contain approximately 40 subjects. With Revised Protocol 06, no new subjects will be randomized in the anogenital HPV associated tumors cohorts.

Additionally, the metastatic cervical Combination B cohort will be expanded to treat approximately 50 subjects as first-line treatment for their recurrent/metastatic disease if unfit or unsuitable to receive platinum-based therapy and approximately 20 subjects as second-line treatment for their recurrent/metastatic SCC of the cervix to confirm the efficacy signal. With Combo B and the Combo B expansion, there should be a total of approximately 75 subjects with first-line treatment and approximately 35 subjects with second-line treatment of cervical cancer (approximately 110 cervical subjects total).

The HPV+ SCCHN with prior PD-1/PD-L1 treatment tumor type will be enrolled in Metastatic Combination Cohort (Combo C). Combo C will contain approximately 40 subjects. However, at Revised Protocol 05, no new subjects will be enrolled in this cohort.

Approximately 40 HPV negative and HPV indeterminate I-O naive SCCHN subjects will be enrolled to the Combo D treatment arm. With Revised Protocol 06, no new subjects will be enrolled in this cohort.

Sample sizes of each treatment arm in each tumor type are summarized in [Table 8.1-3](#).

An ORR in excess of 10% will be considered of clinical interest. Assuming the true ORR is 25%, 40 subjects in each tumor type can provide approximately 79.8% power to reject the null hypothesis that the true ORR is 10%, considering a 2-sided alpha of 5%. In addition [Table 8.1-4](#) shows the precision of the estimation of ORR based on the two sided 95% exact CI using Clopper-Pearson methods based on 8, 9, 12, 16 and 20 responders out of 40 subjects. At observed more than or equal to 9 responders, ie, $ORR \geq 22.5\%$, the lower bound of the 95% CI excludes 10%.

[Table 8.1-5](#) shows the precision of the estimation of ORR based on the two sided 95% exact CI using Clopper-Pearson methods based on 1, 2, 3, 4 and 5 responders out of 12 subjects. Assuming the true ORR is 25%, 12 subjects can provide approximately 84% probability to observe at least 2 responders.

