[Table 8.1-6](#) shows the precision of the estimation of ORR based on the two sided 95% exact CI using Clopper-Pearson methods based on 20, 22, 26, 30, 33, and 35 responders out of 50 subjects. At observed more than or equal to 22 responders, ie, $ORR \geq 44\%$, the lower bound of the 95% CI excludes 30%; at observed more than or equal to 26 responders, ie, $ORR \geq 52\%$, the lower bound of the 95% CI excludes 37%.

[Table 8.1-7](#) shows the precision of the estimation of ORR based on the two sided 95% exact CI using Clopper-Pearson methods based on 3, 5, 8, 10, 12 and 14 responders out of 35 subjects. At observed more than or equal to 8 responders, ie, $ORR \geq 22.9\%$, the lower bound of the 95% CI excludes 10%.

Due to the low prevalence of EBV+ Gastric tumor types and the current investigation of this tumor type in other BMS-sponsored studies, combination cohorts in this study will no longer include EBV+ Gastric tumor type.

Table 8.1-3: Sample Size in Recurrent/Metastatic Combination Cohort

| | Combo A Nivo-3mg/kg q2w + Ipi-1mg/kg q6w | Combo B Nivo-1mg/kg + Ipi-3mg/kg q3w x 4 followed by Nivo 240mg q2w | Combo C Nivo+Anti-Lag-3 | Combo D Nivo+Dara |
|---|--|---|----------------------------|----------------------|
| Cervical | 40 | 110 ^a | | |
| Anogenital HPV associated tumors (vaginal/vulvar/anal canal/penile) | 40 | 40 | | |
| MCC | 40 | | | |
| NPC | 40 | | | |
| HPV+ SCCHN (I/O naive) | 40 | | | |
| HPV+ SCCHN (Prior PD-1/PD-L1) | | | 40 | |
| I-O Naive SCCHN | | | | 40 |

^a Includes 40 from Combination B and 70 from Combination B expansion.

Table 8.1-4: Two-sided 95% Exact CI Using Clopper-Pearson Method Based on the Number of Observed Responses out of 40 Subjects

| Number of observed responses | 8 | 9 | 12 | 16 | 20 |
|------------------------------|--------------|--------------|---------------|---------------|---------------|
| Observed Response Rate | 8/40 (20.0%) | 9/40 (22.5%) | 12/40 (30.0%) | 16/40 (40.0%) | 20/40 (50.0%) |
| 95% exact CI (%) | (9.1, 35.6) | (10.8, 38.5) | (16.6, 46.5) | (24.9, 56.7) | (33.8, 66.2) |

Table 8.1-5: Two-sided 95% Exact CI Using Clopper-Pearson Method Based on the Number of Observed Responses out of 12 Subjects

| Number of observed responses | 1 | 2 | 3 | 4 | 5 |
|------------------------------|-------------|--------------|--------------|--------------|--------------|
| Observed Response Rate | 1/12 (8.3%) | 2/12 (16.7%) | 3/12 (25.0%) | 4/12 (33.3%) | 5/12 (41.7%) |

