8.4.2 Efficacy Analyses

8.4.2.1 Primary Endpoint Methods

Neoadjuvant cohort:

- Analyses of drug-related select AEs and drug-related SAEs are discussed in [Section 8.4.3](#)
- Rate of surgery delay will be summarized by binomial response rates and their corresponding two-sided 95% exact CIs using Clopper-Pearson method.

Metastatic cohort (monotherapy and combination therapies):

- The investigator assessed ORR in the metastatic cohort will be summarized by binomial response rates and their corresponding two-sided 95% exact CIs using Clopper-Pearson method.

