7.5.1.2 Metastatic Cohorts: Objective Response Rate

The ORR based on investigator assessment (Per RECIST 1.1) will be summarized. The Clopper-Pearson method will be used to estimate the two-sided 95% confidence intervals.

BOR will be summarized by response category.

To assess consistency of ORR, investigator-assessed ORR (primary analysis) will be summarized for the following subgroups by tumor type:

- Age (descriptive statistics); Age categories (< 65, ≥ 65 and < 75, ≥ 75)
- Gender (Male, Female)
- Race (White, Black, Asian, and Other)
- Region (US/Canada, Europe, Rest of the World)
- ECOG PS (0/1)
- Time from initial disease diagnosis to study entry (<= 1 year, > 1 year)
- Prior therapy (surgery, radiotherapy, and systemic cancer therapy)
- Prior lines of therapy (1, 2, 3, >=4)

- Number of prior therapy in metastatic settings (0, >=1)
- Prior platinum (yes, no) for SCCHN, GYN, cervical, anogenital HPV associated tumors
- Prior bevacizumab (yes, no) for SCCHN, GYN, cervical, anogenital HPV associated tumors
- Time from completion of most recent prior regimen to study entry (<= 3, <3 - <=6, <6 - <=9, <9 - <=12, >12 months)
- All lesions (Investigator tumor assessments at Baseline): sites of diseases, number of disease sites per subject
- Target Lesions (Investigator tumor assessments at Baseline): presence of target lesions, site of target lesion, sum of diameters of target lesions.
- Virus status (Positive / Negative) in tumor types **(M-3)** GYN (cervical, vaginal, and vulva) Carcinoma, **(MC-2a, MC-2b, MC-exp)** Cervical Carcinoma, **(MC-3a, MC-3b)** Anogenital HPV associated tumors (vaginal/vulvar/anal canal/penile), **(M-4, MC-4a)** Merkel Cell Carcinoma and **(M-5,MC-5a)** Nasopharyngeal Carcinoma (NPC), for which the virus status are tested retrospectively.

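### Protocol 8.1 and SAP 5 say 22 of 50 responders excludes a 30% response rate; the exact lower bound is 29.99%, and 23 of 50 is the first count that does

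*Protocol*

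**What the plan says.** Protocol 8.1 plans to expand the cervical Combo B cohort with "approximately 50 subjects as first-line treatment for their recurrent/metastatic disease", plus about 20 second-line subjects. It then illustrates precision in Table 8.1-6 with the "two sided 95% exact CI using Clopper-Pearson methods based on 20, 22, 26, 30, 33, and 35 responders" out of 50. The accompanying sentence reads "At observed more than or equal to 22 responders" (ORR at least 44%) "the lower bound of the 95% CI excludes 30" per cent. It adds that from 26 responders the lower bound excludes 37%.

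Table 8.1-6 prints 30.0 to 58.8 for 22/50. SAP section 5 carries the same sentence, and SAP Table 5-6 prints the same interval.

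The interval method is not in doubt. The tables are captioned as exact Clopper-Pearson. Protocol 8.4.2.1 plans ORR with "corresponding two-sided 95% exact CIs using Clopper-Pearson method", and SAP 7.5.1.2 says the "Clopper-Pearson method will be used to estimate the two-sided 95% confidence intervals".

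Protocol 8.1 also opens with the statement "Sample size determination is not based on statistical power calculation".

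**The concern.** A lower limit printed as 30.0 cannot by itself show that 30% is excluded. The limit has to lie above 30% before rounding. If it does not, both documents give a responder threshold that is one too low under the method they name, and neither corrects the other.

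The result at stake is exactly 22 responders in 50. The plan would say that 30% had been ruled out, while the reported interval would still contain it. Such a result is not remote: its probability is 9.6% if the true ORR is 40% and 11.3% if it is 44%.

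**Working it through.** **Inputs.** n = 50, x = 22, reference rate 30%, and a two-sided 95% Clopper-Pearson interval with 2.5% in each tail. All come from Protocol 8.1 and are repeated in SAP section 5.

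**Formulas.** For x responders in n:

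- lower limit = 0.025 quantile of Beta(x, n − x + 1)
- upper limit = 0.975 quantile of Beta(x + 1, n − x)
- equivalently, the lower limit exceeds 30% if and only if P(X ≥ x | n, 0.30) < 0.025

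**Step 1: reproduce the printed table for n = 50.**

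| Responders | Computed 95% CI (%) | Printed (%) | Agrees |
|---|---|---|---|
| 20 | 26.4078 to 54.8206 | 26.4, 54.8 | yes |
| 22 | 29.9907 to 58.7456 | 30.0, 58.8 | lower only after rounding; upper no |
| 26 | 37.4152 to 66.3395 | 37.4, 66.3 | yes |
| 30 | 45.1794 to 73.5922 | 45.2, 73.6 | yes |
| 33 | 51.2348 to 78.7945 | 51.2, 78.8 | yes |
| 35 | 55.3918 to 82.1382 | 55.4, 82.1 | yes |

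The documents did use Clopper-Pearson; only the 22/50 entry is off. Rounding in two steps would give both printed limits (29.9907 → 29.99 → 30.0 and 58.7456 → 58.75 → 58.8). That would explain the entry, but the documents do not confirm it.

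**Step 2: test the exclusion of 30%.**

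| Responders | Lower limit (%) | P(X ≥ x given 0.30) | Excludes 30%? |
|---|---|---|---|
| 21 | 28.1882 | 0.047764 | no |
| 22 | 29.9907 | 0.025087 | no |
| 23 | 31.8149 | 0.012276 | yes |

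At 22 the limit falls short by 30 − 29.9907 = 0.0093 percentage points, and the tail exceeds 0.025 by 0.000087. Exact rational arithmetic also puts the tail above 0.025, so this is not numerical error. The first count that excludes 30% is 23/50 (46%), with interval 31.8% to 60.7%.

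**Step 3: check the neighbouring statements.** The other three exclusion statements in Protocol 8.1 hold:

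- 26/50 has lower limit 37.42%, above 37% (25/50 gives 35.53%)
- 9/40 has lower limit 10.84%, above 10% (8/40 gives 9.05%)
- 8/35 has lower limit 10.42%, above 10% (7/35 gives 8.44%)

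Tables 8.1-2 and 8.1-4 to 8.1-7 print 3 + 5 + 5 + 6 + 6 = 25 intervals. The other 24 reproduce to the printed decimal.

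**Step 4: see whether another method rescues 22/50.** Lower limits would be 30.24% (Wald), 30.77% (mid-p), 30.90% (Jeffreys), 31.16% (Wilson and Agresti-Coull) and 31.98% (one-sided 95% exact). All exceed 30%, but neither document names any of them for ORR.

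**Step 5: sensitivity to n.** Enrolment is only approximately 50. The lower limit is 30.67% for 22/49 and 29.35% for 22/51.

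**The case against.** The strongest objection concerns weight, not arithmetic. No decision rests on the sentence. The sample size is declared not to be power-based, and the table is offered as a display of precision. The stated ORR benchmarks are above 10%, and 25% or greater; the only stated null is 10%. Neither 30% nor 37% has a formal role. All of this stands, and it makes the point a minor one.

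It can also be said that a report to one decimal would print 30.0 to 58.7, so that no reader would see a limit below 30. That is true of the display, but a limit shown as 30.0 still does not exclude 30%, and the unrounded interval contains it.

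Finally, the situation is narrow. It needs exactly 22 responders and exactly 50 subjects, and 50 is not an analysis cohort listed in SAP 6.3.1. That section lists Combo B and its expansion, with about 40 and 70 subjects. One subject fewer would make the statement true. This also stands, but one subject more widens the shortfall, which is a further reason not to claim exclusion flatly.

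**Conclusion.** The statement is wrong as written in both documents. Under the two-sided 95% Clopper-Pearson interval that they specify, with exactly 50 subjects, 22 responders do not exclude 30%, and 23 do. The error is one responder in the stated threshold, 0.009 percentage points in the lower limit, and one unit in the last printed digit of the upper limit. It is confined to this entry and its sentence. It should be corrected because it is a false threshold for the primary endpoint, repeated in both documents. It does not affect the design, the sample size or the planned analysis.

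**What to change.** In the text for Protocol Table 8.1-6 and for SAP Table 5-6, do one of the following:

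- change the threshold from 22 (44%) to 23 (46%), ideally with a 23/50 column showing 31.8 to 60.7; or
- keep 22/50 and say that the lower bound is approximately 30%, without claiming exclusion.

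In both tables, change the upper limit for 22/50 from 58.8 to 58.7. The protocol synopsis does not carry this sentence, so it needs no edit. The cost is one sentence and one table cell per document, plus one column if the 23/50 interval is added.

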8.2 Populations for Analyses

The analysis populations will be by cohort (neoadjuvant and metastatic), tumor type, and combination regimen. The following populations will be defined, and their specific applications will be documented in detail in the statistical analysis plan:

- All Enrolled Subjects: All subjects who signed an informed consent form and were registered into the IRT.
- All Treated Subjects: All enrolled subjects who received at least one dose of study drug.
 - All Response Evaluable Subjects: All treated subjects in recurrent/metastatic cohorts (monotherapy and combination therapy) who have a BOR of CR, PR, SD, Non-CR/Non-PD or PD, and target lesion(s) assessed at baseline, and one of the following: i) at least one on-study time point (before sub-sequent therapy) with all baseline target lesion(s) assessed; ii) clinical progression or death before any on-study tumor assessment.
 - All Evaluable Neoadjuvant Subjects: All treated subjects in neoadjuvant cohorts who have available paired tissue samples at Screening and Day 29.
- Outcomes Research Subjects: All treated subjects who have an assessment at baseline and at least one post-baseline assessment.
- Pharmacokinetic Subjects: All subjects who receive at least one dose of study drug and have available serum concentration data.

- Immunogenicity Subjects: All treated subjects with baseline and at least 1 post-baseline immunogenicity assessment for nivolumab, ipilimumab and BMS-986016 (relatlimab); All treated subjects with at least 1 post-baseline immunogenicity assessment for daratumumab.
- Biomarker Subjects: All treated subjects who have available biomarker data.

8.3 Endpoints

8.3.1 Primary Endpoint(s)

Neoadjuvant cohort:

- The safety and tolerability objective will be measured by the incidence of drug-related select AEs and drug-related SAEs.
- Rate of surgery delay, which is defined as the proportion of subjects in the neoadjuvant cohort with surgery delayed > 4 weeks from the planned surgery date or planned start date for chemoradiation due to a drug-related AE will be reported for each tumor type.

Metastatic cohorts (monotherapy and combination therapies):

- The investigator-assessed objective response rate (ORR). ORR is defined as the number of subjects with a best overall response (BOR) of confirmed complete response (CR) or partial response (PR) divided by the number of treated subjects. BOR is defined as the best response designation recorded between the date of first dose and the date of the initial objectively documented tumor progression per investigator assessment using RECIST 1.1 criteria or the date of the last tumor assessment date prior to subsequent therapy. In this study, an ORR in excess of 10% will be considered of clinical interest, and an ORR of 25% or greater will be considered of strong clinical interest.

8.3.2 Secondary Endpoint(s)

Metastatic cohorts (monotherapy and combination therapies):

- Duration of response (DOR) is defined as the time from first confirmed response (CR or PR) to the date of the initial objectively documented tumor progression as determined per investigator assessment using RECIST 1.1 criteria or death due to any cause, whichever occurs first. Subjects who did not start subsequent anti-cancer therapy and die without a reported prior progression will be considered to have progressed on the date of their death. Subjects who did not progress or die will be censored on the date of their last tumor assessment. Subjects who did not have any on study tumor assessments and did not die will be censored on the date they were treated. Subjects who started any subsequent anti-cancer therapy prior to death and without a prior reported progression will be censored at the last tumor assessment prior to or on the date of initiation of the subsequent anti-cancer therapy. DOR will only be evaluated in subjects with objective response of CR or PR.
- Overall survival (OS) is defined as the time from first dosing date to the date of death. A subject who has not died will be censored at last known date alive.
- Investigator-assessed progression free survival (PFS) is defined as the time from first dosing date to the date of the first documented tumor progression, as determined by investigators (per

RECIST 1.1), or death due to any cause. Subjects who did not start subsequent anti-cancer therapy and die without a reported prior progression will be considered to have progressed on the date of their death. Subjects who did not progress or die will be censored on the date of their last tumor assessment. Subjects who did not have any on study tumor assessments and did not die will be censored on the date they were treated. Subjects who started any subsequent anti-cancer therapy prior to death and without a prior reported progression will be censored at the last tumor assessment prior to or on the date of initiation of the subsequent anti-cancer therapy.

8.3.3 *Exploratory Endpoint(s)*

Neoadjuvant cohort:

- The percent change from baseline of select immune cells and the percent change from baseline of select immune activation/inhibitory molecules of viral-specific T cells in tumor specific subsets of nivolumab treated subjects will be evaluated.
- Recurrence-free survival (RFS), which is defined as the time from surgery to the date of recurrence(local, regional, metastasis, locally advanced unresectable recurrence, clinical or radiographic progression occurs after surgery) as determined by investigators, or death due to any cause, whichever occurs first. (Note: a subject who dies without reported recurrence will be considered to have recurred on the date of death.) For subjects who remain alive and whose disease has not recurred, RFS will be censored on the date of last evaluable disease assessment. Participants who did not have any post-surgery disease assessments and did not die will be censored on the surgery date. Further details on the censoring rules for consideration of subsequent therapies, will be described in the Statistical Analysis Plan (SAP).
- The proportion of treated subjects who experiences pathologic complete response will be used to determine pathologic response rate of tumors after two doses of neoadjuvant nivolumab in HPV positive and negative SCCHN, resectable Merkel Cell Carcinoma, and cervical, vaginal, or vulvar cancer. Pathological complete response (pCR) is defined as the absence of residual viable invasive cancer on hematoxylin and eosin evaluation of the complete resected tumor specimen and all sampled regional lymph nodes following completion of neoadjuvant systemic therapy.

Metastatic cohorts (monotherapy and combination therapies):

- The safety and tolerability objective will be measured by the incidence of adverse events, serious adverse events, deaths and laboratory abnormalities.
- Pre- and post-treatment EBV DNA levels will be collected in the subjects with EBV positive gastric cancer and nasopharyngeal carcinoma. The change in EBV DNA levels will be used to determine the effect of BMS-936558 (nivolumab). (Monotherapy cohort only)

Neoadjuvant and Metastatic cohorts (monotherapy and combination therapies):

- The PK samples collected will be used to determine summary measures of nivolumab, ipilimumab, BMS-986016 (relatlimab), and daratumumab exposures (see [Section 8.4.4](#))
- Exploratory endpoints for pharmacodynamics, outcomes research and immunogenicity are discussed in detail in [Sections 5.6, 5.7](#) and [5.8](#).

Other exploratory endpoints will be discussed in detail in the statistical analysis plan.

8.4 Analyses

All analyses for neoadjuvant cohort will be performed as it completes safety follow-up. All analyses for each metastatic cohort (nivolumab monotherapy or combo A, B, C, or D) will be performed as it completes efficacy follow-up. All analyses will be performed independently by cohort, by tumor type, and regimen.

The randomization of the patients with metastatic cervical cancer and anogenital HPV associated (vulvar/vaginal/anal canal/penile) tumor types to combo A, B, or D is for administration purposes, not for comparison. Analyses will be done for each dosing schema separately.

